# Assessment of perceptive accuracy for motor performance in persons with multiple sclerosis

## Introduction

The majority of people with multiple sclerosis (PwMS) have impaired gait and sit-to-stand function: they walk slower, with an increased energetic cost of walking and cluster-specific alterations from the physiological gait pattern, while lower limb extensor weakness and diminished postural control have also an impact on their sit-to-stand performance. (1-4)

After sustained activity these impairments tend to increase for a large part of PwMS: motor performance fatigability, the objectively measured acute performance deterioration, may involve both quantitative and qualitative aspects of their motor performance. (5, 6)

This can be a barrier to participation in leisure-time physical activity (PA), creating a vicious circle leading to increase in disability: inactive PwMS walk slower with an increased energetic cost of walking, consequently experiencing more reductions in walking bouts quality and distance in their daily life.

Furthermore, motor performance impairments and levels of PA, in this population, may also be linked to sensory abnormalities, personal beliefs and fluctuations of symptom intensity. (7-11)

Fatigue is the hallmark symptom in MS, with reported prevalence reaching 78%, and PwMS with higher levels of perceived fatigue tend to become less physically active in their daily life, also in absence of motor performance fatigability. (12, 13)

Generally, fatigue is a sense of tiredness and lack of energy that can interfere with a person's usual daily activities and, leading to increase the weighting of effort costs in cost-benefit evaluations, it can be a functional interoceptive signal to stop or modify our activity, take appropriate rests or pace our efforts. (14)

[figure not shown]

Figure 1 The predictive model of bodily states. Illustration of the interoceptive core control network and of the precision weighted inferential process forming perception. Adapted from (15)

The efficiency of this self-regulation system depends on the ability of the central interoceptive core control network to accurately judge our body state (which resources are available versus necessary to achieve a desired outcome) and, when carrying out physical activity, to timely produce allostasis adjustments (i.e. 'actions to maintain the body in homeostasis') through interactions with the

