## Task 2: Perceptive accuracy for STS duration variations during repeated STS postural transitions

The participants will be tested on a armless chair of normalized seat height, for their ability to accurately perceive changes in their self-paced sit to stand duration.

They will be instructed to perform STS repetitions at a fixed pace, but to execute each transition from sitting to standing as fast as possible. Sitting with the back rested on the back-support will be the starting position of the test. After the first STS transition (i.e. starting from the first standing position), they will be presented with a countdown of 10 seconds during which they must return to the sitting position and, from that position, perform the following STS transition. The participant will be asked to use the time in between STS repetitions to evaluate their sit-to-stand duration, comparing it with the previous, and decide if to report (or not) a change in STS duration (using the same handheld sensor as during the 6MWT). The STS execution will be stopped by the examiner after 36 repetitions.

Neutral instructions will be provided to the subject before starting the STS test by reading the following script: "When you will hear the beep tone, squeeze the sensor and start performing sit-to-stand repetitions, doing each of them standing up at the maximal speed that you can use to stand up safely. Be aware that we are not asking you to perform as many repetitions you can in a limited amount of time, but that you will be asked to stand up from the chair once every 10 seconds, you just have to do each repetition at your maximal speed: going from sitting to standing as fast as you can. Natural variations in your sit-to-stand speed may occur between repetitions. We want you to notice and, starting from the second repetition, report them using the handheld sensor: if you perceived a change in the time needed to stand up, being it shorter or longer does not matter (you will not have to indicate it), squeeze the sensor in your hand during the resting phase. In between repetitions you will have 10 seconds to decide if to report a change: in the case you didn't notice any change, simply don't squeeze."

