Participants will be also equipped with headphones. Using the same set of wearable sensors, as in task 1 (6MWT overground), to detect motor performance will allow us to then confront the time and frequency of the reports with the actual STS duration variations, and propose novel outcome measures: a perceptive threshold for STS duration changes and the ratio between reporting frequency and actual STS duration variability, reflecting perceptive accuracy (see example plot from piloting in Figure 8). The intensity of perceived fatigue and a short structured interview will follow in the same way as in task 1 (6MWT overground).

[figure not shown]

Figure 8 Perceptive accuracy for STS duration variations during repeated STS postural transitions: Task 2 illustration, wearables placement and Perception vs Performance plot graphic illustration.

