## Data and statistical analysis

Motor performance data (gait and STS kinematic, kinetics and spatial-temporal parameters) will be acquired by wearable sensors and extracted from Moveo software (APDM) as .csv file or raw data, and Matlab scripts will be used in case of parameters requiring specific calculation. Data acquired from the participants reports on their perception, during the experimental tasks in Part A and Part B, will be extracted with dedicated Matlab scripts. Statistical analysis will be performed using SPSS (V. 28.01). Tests of normality (Shapiro-Wilk test) will be used to determine if parametric or non-parametric statistical tests have to be used for the comparisons and correlations. The  $\alpha$  for all analyses will be set at 0,05.

**Clinical assessment** outcomes, with a particular focus on the MAIA-2, ISAQ and PAS scores and subscores, will be compared between groups with an independent T test (or with its non-parametric equivalent Mann-Whitney U-Test), to detect significant differences in the subjective beliefs about perceptive abilities.

In the **experimental Part A** we will obtain the participants' minimal perceptive threshold for self-paced performance variations which will be compared between groups with an independent T test (or with its non-parametric equivalent). We will also relate the frequency of the reports with the measured performance variability (coefficient of variation of the selected motor performance parameter: gait speed or STS duration) to obtain a novel outcome measure reflecting perceptive accuracy. We will study it between and within groups using a mixed model ANOVA with time and group as factors to detect significant differences between PwMS and controls and its variations relative to the accumulation of fatigue during the prolonged motor tasks. To investigate its interference with perceptive accuracy the difference between the subjective rate of fatigue (VAS-F) pre-post task protocols will be included in the analysis as covariate.

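### Part A sit-to-stand duration ratio: participants judge each stand against the previous one, but the CV in the denominator also counts gradual slowing, so over the whole task or long blocks a participant who slows can score lower at identical perception

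*Combined protocol and SAP*

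**What the plan says.** The Part A section on Task 2 (STS duration) asks the participant, between stands, to "evaluate their sit-to-stand duration, comparing it with the previous, and decide if to report (or not) a change in STS duration". The pace is fixed, since "you will be asked to stand up from the chair once every 10 seconds", and "The STS execution will be stopped by the examiner after 36 repetitions". That is 36 x 10 s = 6 minutes, with 35 possible judgements because reporting starts at the second stand.

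The same section proposes as outcome "the ratio between reporting frequency and actual STS duration variability, reflecting perceptive accuracy". Under Data and statistical analysis, variability is defined as the "coefficient of variation of the selected motor performance parameter: gait speed or STS duration". The ratio then goes into a "mixed model ANOVA with time and group as factors", and "the difference between the subjective rate of fatigue (VAS-F) pre-post task protocols will be included in the analysis as covariate". The last paragraph of that section adds correlations and a regression of the accuracy outcomes on demographics, questionnaires and clinical assessments.

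The plan does not define the time blocks, the window over which the CV is taken, any detrending, or any measure of successive change.

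**The concern.** The numerator counts perceived changes between neighbouring stands. The denominator is blind to order: the same 36 durations have the same CV whether they rise smoothly or are shuffled, although the changes between neighbours differ greatly. Steady slowing therefore raises the denominator and gives the participant almost nothing to report. Someone who follows the instruction perfectly can get a lower ratio only because they slow down.

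The Introduction expects such slowing in many PwMS: "motor performance fatigability, the objectively measured acute performance deterioration, may involve both quantitative and qualitative aspects of their motor performance". The Part A hypothesis expects lower accuracy in PwMS with higher reported fatigue. Motor fatigability could then be read as poor perception, both in the group comparison and in the closing correlations with fatigue measures. The fatigue covariate is a subjective rating before and after the task. It is not the measured slowing, so it does not remove this effect by design.

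**Working it through.** The plan gives no value for the ratio, the CV, the slowing or the report rate, so there is no figure of its own to reproduce.

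**Inputs.** From the documents: 36 stands, 35 judgements, each against the previous stand. Assumed: linear slowing D from first to last stand of 10-20%; independent proportional noise s of 4-8%; an ideal perceiver who reports every successive change above 8%.

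**Numerator.** Slowing of 20% is 20%/35 = 0.57% per stand. At s = 6% the difference between neighbours has SD 6% x sqrt(2) = 8.5%, so the report frequency is 2 x [1 - Phi(8/8.5)], about 0.35. A shift of 0.57% leaves it at 0.35.

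**Whole-task CV.** A linear ramp over n = 36 stands adds (D/35)^2 x n(n+1)/12 = 111 x (D/35)^2 to the sample variance, and the mean duration becomes 1 + D/2. So:

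CV^2 is about s^2 + 111 x (D/35)^2 / (1 + D/2)^2

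The added term is 0.000906/1.1025 = 0.000822 at D = 10%, and 0.003624/1.21 = 0.002995 at D = 20%. The ratio is multiplied by s/CV. For s = 6% and D = 20%: 0.06/sqrt(0.0036 + 0.002995) = 0.06/0.0812 = 0.74.

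| Noise s | Slowing D | Fall in ratio, formula | Fall in ratio, simulated |
|---|---|---|---|
| 4% | 10% | 19% | 17% |
| 4% | 20% | 41% | 39% |
| 6% | 10% | 10% | 9% |
| 6% | 20% | 26% | 25% |
| 8% | 10% | 6% | 6% |
| 8% | 20% | 17% | 17% |

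At s = 6% the simulated ratio goes from 5.77 with no slowing to about 5.2 (10%) and 4.3 (20%). The first step is about 0.4 between-person SD.

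**Shorter windows.** The ramp factor n(n+1)/12 drops from 111 to 28.5 for halves (18 stands) and to 3.5 for minutes (6 stands). At 20% slowing the simulated fall is 5-15% in halves and about 1% or less per minute. The formula puts the per-minute fall at 1-3%. If the reports in each block are divided by a whole-task CV, the full effect stays.

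**Matching denominator.** Write RMSSD for the root mean square of successive differences. Then RMSSD^2/2 is about s^2 + (D/35)^2/2. At s = 6% and D = 20% the added term is 0.0000163 against 0.0036, which moves the ratio by about 0.2%. Simulated ratios stay at 5.77-5.79 for slowing up to 30%.

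**Effect on a test.** A separate simulation used a noisy observer, a 10% threshold, s = 5% and 40 per group, with slowing as the only group difference. A t test on the whole-task ratio rejected in 19%, 43% and 74% of runs at 10%, 15% and 20% slowing, against 5-6% with the matching denominator. It simplifies the planned ANOVA and lets everyone in one group slow.

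**What remains.** With the matching denominator and no slowing, the same perceiver scores about 3.85 at s = 4% and 5.78 at s = 6%.

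**The case against.** The strongest reply is that the plan analyses this ratio with time as a factor, so it must exist in several blocks. Six minutes of six stands suggests minutes as the blocks. If reports and CV are both taken per minute, slowing nearly drops out, and averaging the blocks gives the single value per person that the correlations need. A reader might therefore infer from the mismatch that people who slow will be scored as less accurate whatever is done. The documents do not support that. They also do not rule it out: the Part A blocks are undefined, the minute-by-minute wording belongs to Part B, halves keep part of the effect, and a CV from six stands is imprecise.

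A second reply concerns direction. A reader might infer a sure bias toward the hypothesis. That needs equal repetition noise across groups, which the documents do not state. An identical perceiver with 4% noise and no slowing scores about 3.9, while one with 6% noise and 20% slowing scores about 4.3. If PwMS are also more variable, the net bias could run the other way. The hypothesis also concerns reported fatigue, and the Introduction allows perceived fatigue without motor fatigability.

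Third, the sizes are assumed. At 5% slowing and 6% noise the whole-task fall is under 3%. The plan also never says that a higher ratio means better accuracy, although that is its natural reading. These points limit the size and certainty of the effect. They do not remove the mismatch between the instructed judgement and the denominator.

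**Conclusion.** The concern holds in conditional form. For STS duration, the denominator counts drift that the participant was not asked to judge, and the unstated window decides whether this matters. Under the assumptions above, a steadily slowing participant with identical perception scores about 6-39% lower with a whole-task CV, about 5-15% lower in halves at 20% slowing, and about 1% or less per minute. With equal noise across groups and more slowing in PwMS, this would favour the hypothesis and could make fatigability look like poor perception in the closing correlations. With unequal noise the net direction is not determined.

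Two further inferences go too far. The CV is named only for gait speed and STS duration, so the smoothness run has no stated denominator to call wrong. And removing drift does not make the ratio a pure measure of perception, because its dependence on repetition noise (about 3.85 against 5.78, roughly 50%) exceeds the 9-25% drift effect at 6% noise. The study is exploratory and the outcome new, so this should be settled before the data are scored; it does not threaten the design.

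**What to change.** In Data and statistical analysis, for the STS duration ratio:

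- Use RMSSD/(sqrt(2) x mean) as the denominator, or a linearly detrended CV. With independent noise and no drift, both match the ordinary CV in expectation.
- Compute reports and denominator over the same window, and state that window, both for the ANOVA blocks and for the single value per person in the correlations.
- Report linear slowing over the 36 stands separately, as the fatigability measure.
- Use the same form in the smoothness run if a variability ratio is computed there.

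The cost is about one line in the plan and one line of Matlab, with no new data and no change to the tasks. There are two downsides, and the plan should state both. The denominator will differ from that of the walking task, and the ratio will still vary with a person's repetition noise, which this change does not correct.

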## Methodology

### Participants

44 PwMS and 44 healthy controls (40, +10% to cover possible dropouts and missing data) will be recruited from the Flemish MS rehabilitation centers in Melsbroek (NMSC) and Pelt (Noorderhart RMSC), and as well from the REVAL research center in UHasselt and its established network (eg. UMSC Patient Platform). Information flyers will be distributed in the centers and online content via the website and social media of REVAL and the Flemish MS society; no economical compensation will be provided by the research organization to the participants of this study. We will search age and sex-matching subjects for the healthy controls, considering a 5-year range per subject. After giving informed consent, demographics of age and gender, height and weight, years of education, as well as MS-related information such as EDSS, type of MS, use of assistive device for walking in daily life, and years since diagnosis, will be collected and provided by the centers or via self-report. The participants will be instructed to keep their normal routine but to avoid extraneous physical activity at least 24 hours before the data collection session.

- Inclusion criteria for PwMS: age between 18 and 65 years old; a diagnosis of MS (2017 revisions of the McDonalds criteria); ability to walk for 6 minutes without rest and without the need of a walking aid; ability to repeatedly perform the sit to stand transitions on a standard chair (43cm seat height) without hand support. Additionally, no relapses >1 month preceding the start of the study.
- Inclusion criteria for healthy controls: age between 18 and 70 years old, sex- and age-matched on a group level.
- Exclusion criteria: cognitive impairment hindering understanding of study instructions, pregnancy, and musculoskeletal disorders in the lower limbs (not related to MS), cardiovascular red flags for exercise (screened with Physical Activity Readiness Questionnaire), other diagnosis for neurological or metabolic disease limiting the full execution of the tests (eg. peripheral neuropathy altering the foot plantar sensibility).

Inclusion/exclusion criteria will be controlled at the beginning of the first session: the participant will read the criteria presented in the informed consent and will be asked to confirm that he/she can enroll in the study.

[figure not shown]

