Participants will be also equipped with noise-cancelling headphones to avoid auditory perception of steps rhythm and influence of possible environmental distractions. Using wearable sensors to detect motor performance (spatiotemporal and kinematic parameter detected with a configuration of 6 OPALS – technology© IMU sensors: 2 over the dorsal part of the feet, 2 on the lower legs, 1 anterior to the sternum and 1 posterior to the third/fourth lumbar vertebra, see figure 4) will allow us to then compare the time and frequency of the reports with the actual speed variations, cutting out the steps executed while turning, and propose novel outcome measures: the change in speed at the first report as a perceptive threshold for overground walking speed changes, informing on the minimal clinically important change, and the ratio between reporting frequency and actual speed variability, reflecting perceptive accuracy (see example plot in Figure 6).

[figure not shown]

Figure 6 Perceptive accuracy for walking speed variations during overground 6MWT: Task 1 illustration, wearables placement and Perception vs Performance plot graphic illustration

The intensity of perceived fatigue will be asked just before and immediately after the test using the VAS-F (see Figure 4). Furthermore, a short structured interview will follow including the following question: "On a scale from 0 to 100, how certain are you that you have been precise/accurate in detecting ongoing variations in your performance? Please mark your confidence level on the presented visual scale". This question is then followed by an open-ended question where the participant is asked to report on which sensory information he/she was relying to gauge performance variations and give the reports: "On which aspects of your motor performance where you paying attention to detect variations and decide to give a report during the task? Please list them here".

[figure not shown]

Figure 7 Visual scale for confidence rating: subjective beliefs on their perceptive accuracy

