In the **experimental Part B** within-subject correlations will be calculated between the imposed performance in motor tasks and the perception of its variations. These correlations will be examined separately for different phases of each trial to index perceptive accuracy. Fisher Z transformations (or other types of transformations eg. log transformation) will be applied to these correlations before further analysis, with results back-transformed for reporting. We will study it between and within groups using a mixed model ANOVA with time (protocol subphase) and group as factors to detect significant differences between PwMS and controls and its variations relative to the different subphases of the protocol. To investigate its interference with perceptive accuracy the difference between the subjective rate of fatigue (VAS-F) pre-post protocols will be included in the analysis as covariate. The correspondence between measured and reported dimensions of perceptive accuracy will be calculated as their absolute difference and compared between groups using an independent T test (or with its non-parametric equivalent).

Finally, for the accuracy outcomes derived from both experimental parts we will explore correlations, separated per group, to investigate the relationship between objectively measured perceptive accuracy and factors that potentially interfere with it (demographics, questionnaires and clinical assessments). Then, a regression analysis will be performed to assess the strength of these relationships and identify the most important explanatory factors or predictors.

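### Part B: the per-subphase correlation is undefined when reports or imposed speed are constant, and a repeated-measures ANOVA would then drop the participant from every subphase

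*Combined protocol and SAP*

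**What the plan says.** Under Data and statistical analysis, Part B correlates the imposed level with the perceived level within each participant, separately by phase. The correlations are transformed (Fisher Z or another transformation) and entered in a "mixed model ANOVA with time (protocol subphase) and group as factors", with the pre-post change in VAS-F as covariate. The software is SPSS. No procedure, random effect, covariance structure or estimation method is named.

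Part B, Task 1 splits the six-minute treadmill protocol into one minute at constant speed, 150 seconds of rising speed and 150 seconds of falling speed, with a verbal report every 10 seconds. The scripts for the treadmill and seat-height tasks both tell participants that they may feel no variation at all.

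The only provision for incomplete data is in Participants: "44 PwMS and 44 healthy controls (40, +10% to cover possible dropouts and missing data) will be recruited". There is no rule for an undefined correlation or a missing subphase.

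Part A also uses a "mixed model ANOVA with time and group as factors", but its outcome is "the ratio between reporting frequency and actual speed variability, reflecting perceptive accuracy".

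**The concern.** A between-within ANOVA run through the SPSS repeated-measures routine uses only participants with a value at every time level. In Part B two ordinary situations leave a cell empty: the participant gives the same report throughout a subphase, or the imposed level does not move during it.

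The first situation is informative. A participant who notices nothing during a ramp is a poor perceiver, yet would leave the analysis, including the subphases where a value exists. Part B hypothesises lower accuracy in PwMS with more fatigue, and a larger deficit in the last subphase. Removing the least perceptive participants works against detecting either.

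The second situation has nothing to do with perception. It affects everyone in the stable treadmill phase.

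**Working it through.** **Inputs from the documents.** 40 per group plus 10% (Participants). Treadmill phases of 60, 150 and 150 seconds and a report every 10 seconds (Part B, Task 1), hence 6, 15 and 15 reports. Group-by-subphase ANOVA on the correlations (Data and statistical analysis).

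**Assumed, because the documents give no figure.** A per-cell missing rate p of 2% to 5%, independent between subphases, and a true group difference of 0.63 SD. That difference is what 40 per group detects with 80% power at two-sided 5%: (1.960 + 0.842) × √(2/40) = 0.626.

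**1. The plan's own figure.** 40 × 1.10 = 44, as stated. Falling back to 40 means losing 4/44 = 9.1% of those recruited.

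**2. When the index exists.** With x the imposed and y the reported level, r = Σ(x − x̄)(y − ȳ) / √[Σ(x − x̄)² Σ(y − ȳ)²].
- Constant reports: every y − ȳ = 0, so r = 0/0, undefined.
- Constant imposed speed: every x − x̄ = 0, so r = 0/0 whatever the participant reports. In the stable treadmill phase this holds for 88 of 88 participants. If that phase is a level of the subphase factor, listwise deletion leaves 0 of 88.
- At the other extreme, r = 1 gives an infinite Fisher Z, so very accurate participants can also yield an unusable value.

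**3. Participants lost under listwise deletion.** Complete cases per group = 44 × (1 − p)^k for k subphases.

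| k | p = 2% | p = 5% | largest p that keeps 40 of 44 |
|---|---|---|---|
| 3 | 44 × 0.9412 = 41.4 (5.9% lost) | 44 × 0.8574 = 37.7 (14.3% lost) | 1 − (40/44)^(1/3) = 3.1% |
| 2 | 44 × 0.9604 = 42.3 (4.0% lost) | 44 × 0.9025 = 39.7 (9.8% lost) | 1 − (40/44)^(1/2) = 4.7% |

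The k = 3 row illustrates three usable subphases. On the treadmill only the two ramps can give a correlation, so k = 2 applies once the stable phase is left out.

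**4. Effect of selective loss.** Take two normal distributions with SD 1 and means 0.63 apart, and remove the lowest-accuracy share of the pooled sample.

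| Share removed | Controls left of 44 | PwMS left of 44 | Observed difference (SD) |
|---|---|---|---|
| 5% | 43.1 | 40.5 | 0.52 |
| 10% | 41.9 | 37.3 | 0.46 |
| 20% | 38.9 | 31.5 | 0.38 |

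This shows the direction of the bias. It does not predict its size.

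**5. Part A.** The outcome puts report frequency over variability. No squeeze is a valid response meaning no perceived change, so zero reports gives 0/CV = 0, a defined value. The first-report threshold is undefined without a report, but it goes to a t test, not to the ANOVA.

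**The case against.** Four points can be made against this, and each limits what may be concluded.

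- **Procedure.** A reader might infer that the plan certainly drops incomplete participants. It does not say so: the wording is compatible with SPSS MIXED, which keeps them. The repeated-measures routine is the natural reading, because the text describes an ANOVA with two factors and a covariate and mentions no likelihood estimation. It remains a reading. Under either one, a rule for undefined cells is absent.
- **Cause.** A reader might infer that cells go missing only when perception is poor. The stable phase refutes that, and so does a plateau at the personal maximum speed, which depends on the participant's speed range. Sensor or recording loss may also be unrelated to perception.
- **Scope.** A reader might extend the point to Part A. The undefined-correlation mechanism is absent there, as step 5 shows.
- **Size.** Each ramp yields about 15 solicited reports, soon after familiarization with the range, and all must be identical for r to fail. That may be rare. Independence is also an assumption: if empty cells cluster in the same people, fewer participants are lost than step 3 gives. At 2% over three subphases the loss is within the allowance, so it cannot be said that the allowance will be exceeded.

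What stands is that the scripts foresee constant reports, the stable phase is undefined for everyone, and the analysis section deals with neither.

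**Conclusion.** The point holds for Part B. One part follows from the definition alone: no correlation can be computed in the stable treadmill phase, so that phase cannot be a level of the factor for this index. The other part is conditional. If the repeated-measures routine is used, one undefined subphase costs the whole participant, and losses due to constant reports fall on poor perceivers and can pull the group difference toward zero.

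Neither the frequency nor the resulting bias can be derived from the documents. The range of 6% to 14% lost over three subphases rests on independent cells missing at 2% to 5%, and the shrinkage from 0.63 SD on an assumed difference and strict removal of the lowest values. The study calls itself exploratory, so this is a change that should be made before analysis rather than a flaw that invalidates the design. It matters most for the last-subphase hypothesis.

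**What to change.** Change the Part B paragraph of Data and statistical analysis as follows.

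1. Name the levels of the subphase factor for each task and, for the correlation, limit them to phases in which the imposed level varies.
2. Replace the ANOVA by a linear mixed model on all available cells: SPSS MIXED, REML, random participant intercept, fixed group, subphase and their interaction, and the planned VAS-F covariate. Each participant with at least one defined cell then contributes.
3. Analyse the mean absolute error between perceived and imposed level, on a common scale, for all participants in all subphases as a parallel or sensitivity outcome. It should never be substituted only where r is undefined: that would mix two scales running in opposite directions, since a high r is good and a high error is bad.
4. Report the number of undefined cells by group, subphase and reason.

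The cost is SAP wording and slightly more analysis, with the same software and no new data. The mixed model alone does not remove bias if missingness depends on unobserved accuracy, and it cannot use someone with no defined cell; step 3 is needed for that reason. Absolute error also reflects calibration, not only tracking, so the two results need not agree.

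In Part A the same model would only guard against early stopping or sensor loss.
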